Hydraulic MPKs consist of an integrated microprocessor-controlled linear hydraulic system in combination with a control algorithm. They generate knee joint resistances hydraulically with microprocessor-controlled, motorized valves. This enables continuous variations in the hydraulic resistance to be set for both movement directions. The magnetorheological fluid creates shear forces in comparison to an increase of pressure in a hydraulic system. The increased system pressure can lead to higher temperatures and risk of leakage.

The previous version of the investigational device (RK III/RK XC) features the same intended use, same clinical purpose, same user population, same placement below the socket, uses a battery powered system and is controlled through a software application that can be user configured through a separate computer interface/mobile device. The investigational device is an enhancement of the previous version, functional features and indication are equivalent to previous version and the same critical functions apply. Features that have been added include a mechanical stance locking feature that allows the user to manually lock the knee in 3 different positions in stance and the device will be waterproof. The investigational device also includes functions that were only included in the Rheo Knee XC configuration of the previous version; automatic cycling and running detection and a stair ascent mode.

Results of a pilot stage exploratory clinical investigation including 25 subjects indicate that the investigational device had similar or better performance compared to previous versions of the Rheo knee regarding satisfaction on descending activities. This investigation is designed primarily to confirm these indications and that the performance of the investigational device regarding descending activities is comparable/no worse than Rheo Knee or hydraulic MPKs.

Study Design

[figure not shown]

Figure 2 - Study design and instruments

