Repeated measures analysis has the advantage of increased power compared to group allocations and reduction in error variance associated with individual difference, as each subject acts as its own control. This is important for studying amputees as the group is a small proportion of the total population, and with specific inclusion/exclusion criteria the total eligible population becomes very small, making it difficult to find and recruit subjects to attain an acceptable level of power. This limited population pool often results in a slightly heterogeneous sample, as the amputees available are few and far between, in every sense. Furthermore, no single amputation procedure and therefore amputated stump is exactly the same, making the experience of each amputee unique. The within-subject design significantly reduces the individual differences when comparing the two conditions.

Several studies have provided evidence for the clinical performance of previous versions of the Rheo Knee, which is equivalent to the investigational device and has the same function and intended use, those are detailed in the Literature review device report [1]. The current study is due to a design iteration after modifications to the device from the previous study CIP2022022514 [9].

[figure not shown]
For full details of existing clinical data and pre-clinical data on the investigational device see Investigators Brochure [2].

7 Objectives and Hypotheses

In this trial, the primary objective is to evaluate the efficacy of the investigational device compared to the former Version Rheo Knee (XC) and in addition (mandatory) to other passive MPKs (e.g. C-leg 4, Genium, X3, Plié 3, Orion 3, Quattro, Allux) regarding performance improvements and satisfaction in descending activities for moderate to high active prosthesis users within the intended population for the investigational device.

Additionally, the overall satisfaction for activities of daily living will be evaluated after a certain time of use (4 weeks home use).

The following clinical claims/MNBA items as defined in the Clinical evaluation plan [3] are to be evaluated:

The hypothesis and endpoints are specified in Table 4 and Table 5.

For all hypothesis:

[figure not shown]
μ_1 is average of measurements at baseline (comparator);

[figure not shown]
μ_2 is the average of measurements at 4 week follow up (investigational device);

Table 5 - Endpoints, test methods and hypotheses

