	Hypothesis	Construct & Test Methods	Endpoints	Acceptance Criteria
A	Navii shows better or no worse results in Ramp, Stairs and Level Ground activities compared to prescribed prosthesis	Specific questions (see Annex 8.8)	Rating: Same, better, worse	Overall results for Navii are same or better than for Rheo Knee, with no more than 20% rating it worse, overall for all questions.
B	Navii shows a good level of overall satisfaction in activities of daily living	Subset of PEQ (see Annex 8.4) Specific Questions (see Annex 8.8)	PEQ Rating	Comparison Subset PEQ pre vs post. Navii not worse than prescribed.
C	Mobility is no worse with Navii compared to prescribed MPK	2 MWT	Distance walked in 2MWT (meters)	No significant reduction in distance walked on 2MWT with prescribed knee/Navii
D	Balance during ambulation is no worse with Navii compared to prescribed MPK	TUG	Time to complete TUG (seconds)	No significant increase in time needed to complete TUG with prescribed knee/Navii
E	Mobility is no worse with Navii compared to prescribed MPK	PlusM	PlusM Score	No significant reduction in PlusM Score with prescribed knee/Navii
F	Gather experiences on perceived safety and balance with Navii compared to prescribed knee.	ABC	ABC Score (0-100%)	Acceptable patient-reported perceived safety and performance

7.1 Additional Outcome measures:

8 Design of the Clinical Investigation

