8.1 General

The test will be a non-randomized single group repeated measures open label prospective design with observational and self-report measures.

Amputees are a small proportion of the general population. The population group specified in the inclusion/exclusion criteria is a further subsample of amputees. For practical reasons, i.e. to achieve statistical power, it is therefore more feasible to use within-subject comparison rather than creating study arms to compare. Furthermore, as mobile amputees generally have and use a prosthetic device for their daily activities, within-comparison is feasible comparing to the subject's previous device.

All investigational activities will be conducted at the Össur Orlando site.

As stated above the primary endpoint is Satisfaction on descending stairs, see Table 5, and the secondary endpoints are satisfaction on descending ramps, balance confidence and standing comfort in that respective order of significance. In addition, there are two exploratory endpoints on mobility and balance during ambulation. See previous chapter on objectives and hypothesis and Table 5 for rationale.

Drop-outs and withdrawals will not be replaced.

Instruments for data collection will include the following:

The Prosthesis Evaluation Questionnaire (PEQ) measures prosthetic-related quality of life. It consists of 82 items grouped into nine subscales. In addition, there are individual questions not contained in the subscales regarding satisfaction, pain, transfers, prosthetic care, self-efficacy, and importance¹⁸. This study will include a set of subscales from the PEQ, including specific questions on descending activities.

TUG The Timed Up and Go (TUG) is a tool used to test basic mobility skills by asking the subject to stand up from a chair (which should not be leaned up against a wall), walk a distance of 3 meters, turn around, walk back to the chair and sit down

2MWT is a measurement of endurance that assesses walking distance over two minutes.

ABC is a Patient-reported outcome measure that asks individuals to rate how confident they are that they will not lose their balance while performing 16 different activities.

PLUS-M (Prosthetic Limb Users Survey of Mobility) is a self-report instrument for measuring mobility of adults with lower limb amputation.

Specific questionnaire: In-house generated questionnaire on specific features in the investigational device.

Log file: User should log device use and events.

Video

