10.1 Statistical design and procedures

The primary hypothesis will be assessed with descriptive statistics only, comparing the rates prior-evaluation (current device) and post-evaluation (investigational device). For hypotheses B, C, D, E will be assessed with mixed models effects where MPK type is used as fixed effect, subgroup analysis, and subject as random effect. F will be assessed with exploratory methods. All data will be analyzed exploratively for subgroup effects for input into further studies but not used to support claims.

Acceptance criteria for the data, as applicable, is defined in Table 4 **Endpoints, test methods and hypotheses**. Subgroup analysis will not be performed as no subgroups are defined.

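### Table 5 rows C, D and E accept a no-worse claim because a test is non-significant, with no margin in the readable text

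*Combined protocol and SAP*

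**What the plan says.** Section 7, Table 5 gives these acceptance criteria for the three no-worse hypotheses:

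- Row C, mobility by 2MWT: "No significant reduction in distance walked on 2MWT with prescribed knee/Navii".
- Row D, balance during ambulation by TUG: "No significant increase in time needed to complete TUG with prescribed knee/Navii".
- Row E, mobility by PLUS-M: "No significant reduction in PlusM Score with prescribed knee/Navii".

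On the analysis, section 10.1 says: "For hypotheses B, C, D, E will be assessed with mixed models effects". MPK type is the fixed effect and subject the random effect. It gives no alpha, sidedness or margin.

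Section 10.2 describes a convenience sample of up to 13 and refers the reader to Table 4 for pass/fail criteria. Section 8.3 requires at least 10 completers and cites 10.2 for that figure, but 10.2 does not contain it. Section 8.1 says drop-outs are not replaced.

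Two passages bear on how much rests on these rows. Section 6, after describing pilot results on descending activities, says: "This investigation is designed primarily to confirm these indications". Section 8.1 adds: "In addition, there are two exploratory endpoints on mobility and balance during ambulation".

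Not everything can be read. Section 7 states: "The hypothesis and endpoints are specified in Table 4 and Table 5". Table 4, figures after the words introducing the hypotheses, and the annex are not visible. Sections 10.1 and 10.2 cite Table 4 under the title that Table 5 carries, so it may be the same table misnumbered.

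**The concern.** A no-worse conclusion needs two things: a stated loss that would be tolerable, and a confidence limit that excludes it. Rows C to E use neither. They treat failure to detect a worsening as evidence that there is none.

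The incentive also runs the wrong way. Losing completers or measuring less precisely widens the interval, lowers the chance of significance and so raises the chance of passing. With 10 to 13 subjects this effect is not small.

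Followed as written, the plan could report that mobility or balance is no worse with Navii without having ruled out a loss of any stated size.

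**Working it through.** The plan contains no power or precision calculation, so there is no figure of its own to reproduce.

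**Inputs from the documents.** n = 10 (minimum completers, section 8.3) and n = 13 (maximum, section 10.2); each subject measured on both devices; pass if the worsening is not significant (Table 5).

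**Assumptions, none given in the documents.** A paired t-test at 5% stands in for the mixed model of section 10.1; the differences are normal; each endpoint is taken alone. The true loss d is in units of the SD of the paired difference.

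**1. Probability of passing despite a true loss.** P(pass) = F(t_crit; df = n−1, ncp = d√n), where F is the noncentral t distribution function. The critical values at n = 10 / 13 are 2.262 / 2.179 two-sided and 1.833 / 1.782 one-sided. For d = 0.5 the noncentrality is 0.5√10 = 1.581 and 0.5√13 = 1.803.

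| True loss | Two-sided, n = 10 / 13 | One-sided, n = 10 / 13 |
|---|---|---|
| 0.5 SD | 71% / 62% | 57% / 48% |
| 0.8 SD | 38% / 25% | 25% / 14% |
| 1.0 SD | 20% / 9% | 10% / 4% |

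Simulation at 0.5 SD agrees to within 0.3 percentage points.

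**2. Which SD is meant.** Section 6 stresses that "The within-subject design significantly reduces the individual differences when comparing the two conditions", so the SD basis matters. If the 0.5 SD loss is in between-subject SDs (equal on both devices), then d = 0.5/√(2(1−ρ)), with ρ the within-subject correlation. The ranges below cover both n and both sidedness choices.

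| ρ | d | Pass rate |
|---|---|---|
| 0.3 | 0.423 | 58–78% |
| 0.5 | 0.500 | 48–71% |
| 0.7 | 0.645 | 29–55% |
| 0.8 | 0.791 | 15–39% |
| 0.9 | 1.118 | 2–12% |

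**3. Noisier data pass more easily.** Hold the raw loss at 0.8 SD and make the SD 50% larger, so d = 0.8/1.5 = 0.533. The pass rate rises as follows:

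- Two-sided: from 38% to 67% (n = 10) and from 25% to 58% (n = 13).
- One-sided: from 25% to 53% (n = 10) and from 14% to 43% (n = 13).

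**4. What a pass leaves open.** The 95% CI half-width is t(0.975, n−1)/√n: 2.262/√10 = 0.72 SD and 2.179/√13 = 0.60 SD. An observed loss just short of that passes the two-sided rule, with a 95% CI running from about 0 to 1.43 SD (n = 10) or 1.21 SD (n = 13) worse.

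**5. What a margin rule could achieve.** With no true difference, the probability that the unfavourable limit excludes a margin m is 1 − F(t_crit; n−1, m√n).

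| Margin | Two-sided 95% limit, n = 10 / 13 | One-sided 95% limit, n = 10 / 13 | Completers for 80% (two-sided / one-sided limit) |
|---|---|---|---|
| 0.5 SD | 29% / 38% | 43% / 52% | 34 / 27 |
| 0.8 SD | 62% / 75% | 75% / 86% | 15 / 12 |
| 1.0 SD | 80% / 91% | 90% / 96% | 10 / 8 |

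**The case against.** **The endpoints are exploratory.** The two constructs named in section 8.1 match the wording of rows C to E, and the primary hypothesis is assessed descriptively, so nothing decisive rests on these rows. This limits the stakes. But 8.1 counts two endpoints against three rows, section 10.1 assigns exploratory methods to row F only, and all three rows carry acceptance criteria. An exploratory endpoint should not return a no-worse verdict.

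**A margin may exist in the unreadable parts.** It may, and its absence from the plan cannot be asserted. A margin stated elsewhere would still conflict with the significance-based criteria that can be read.

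**The percentages rest on the reviewer's assumptions.** This stands. For a loss of 0.5 between-subject SD they run from 78% down to 2% as the correlation goes from 0.3 to 0.9, and the documents do not bound that correlation. It is also unclear whether MPK type in section 10.1 means Navii versus prescribed knee or also distinguishes the prescribed knees; extra terms would cost degrees of freedom and could raise the pass rates slightly. The logical fault needs none of these figures.

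**The fix goes too far or not far enough.** Section 7 says clinical claims are to be evaluated, and the clinical evaluation plan is not available, so the full cost of dropping the statements is unknown. What is given up, however, is a statement the present rule cannot support. Row B also speaks of being not worse without a margin, but it has no significance-based rule and is a separate matter.

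**Conclusion.** The concern holds. As written, rows C, D and E can declare no worse without excluding a loss of any stated size, and the rule rewards small or noisy data. This is an error in the criterion itself, not just missing detail.

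Under the assumed paired t-test at 5%, a true loss of 0.5 SD of the paired difference passes 62–71% of the time two-sided and 48–57% one-sided, for 13 down to 10 completers. Whether such a loss matters clinically cannot be judged, because no SD is given to convert it to metres, seconds or score points.

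It should be fixed, with limited stakes: the trial is aimed primarily at descending activities.

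**What to change.** **Preferred, for rows C, D and E only.** Replace the acceptance criterion and the no-worse conclusion in Table 5 with: *Exploratory. Report the mean paired difference (Navii minus prescribed) with its 95% CI.* Then align the other sections:

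- 8.1: say that all three rows are exploratory.
- 10.2: say that pass/fail criteria do not apply to C, D and E. The expected precision may be added for these rows: a 95% CI half-width of 0.72 to 0.60 SD of the paired difference for 10 to 13 completers.
- 8.3: keep the minimum of 10 and remove only its reference to 10.2.

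*Cost:* no extra subjects or measurements, but the no-worse statements for these rows are given up. Because endpoints change, simple notification under section 11.1 is not enough; the amendment needs approval by the sponsor and PI/LPI, and ethics review.

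**Alternative, only if enrolment has not begun.** Accept a row only if the unfavourable confidence limit excludes a margin in metres, seconds or score points, with the margin and confidence level fixed and justified beforehand. The study is open-label, so a margin set later could be chosen with results known.

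*Cost:* the same approvals, and a real chance of failing when the devices are equal. A margin of 0.8 to 1.0 SD is feasible within 13 subjects, with a 75–96% chance of success at n = 13. A margin of 0.5 SD is not: success is 38–52% at n = 13, and 80% needs 27 to 34 completers.

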8.1 General

The test will be a non-randomized single group repeated measures open label prospective design with observational and self-report measures.

Amputees are a small proportion of the general population. The population group specified in the inclusion/exclusion criteria is a further subsample of amputees. For practical reasons, i.e. to achieve statistical power, it is therefore more feasible to use within-subject comparison rather than creating study arms to compare. Furthermore, as mobile amputees generally have and use a prosthetic device for their daily activities, within-comparison is feasible comparing to the subject's previous device.

All investigational activities will be conducted at the Össur Orlando site.

As stated above the primary endpoint is Satisfaction on descending stairs, see Table 5, and the secondary endpoints are satisfaction on descending ramps, balance confidence and standing comfort in that respective order of significance. In addition, there are two exploratory endpoints on mobility and balance during ambulation. See previous chapter on objectives and hypothesis and Table 5 for rationale.

Drop-outs and withdrawals will not be replaced.

Instruments for data collection will include the following:

The Prosthesis Evaluation Questionnaire (PEQ) measures prosthetic-related quality of life. It consists of 82 items grouped into nine subscales. In addition, there are individual questions not contained in the subscales regarding satisfaction, pain, transfers, prosthetic care, self-efficacy, and importance¹⁸. This study will include a set of subscales from the PEQ, including specific questions on descending activities.

TUG The Timed Up and Go (TUG) is a tool used to test basic mobility skills by asking the subject to stand up from a chair (which should not be leaned up against a wall), walk a distance of 3 meters, turn around, walk back to the chair and sit down

2MWT is a measurement of endurance that assesses walking distance over two minutes.

ABC is a Patient-reported outcome measure that asks individuals to rate how confident they are that they will not lose their balance while performing 16 different activities.

PLUS-M (Prosthetic Limb Users Survey of Mobility) is a self-report instrument for measuring mobility of adults with lower limb amputation.

Specific questionnaire: In-house generated questionnaire on specific features in the investigational device.

Log file: User should log device use and events.

Video

Data logging by Össur Logic

See chapter **10.2 Sample size calculation** for analysis of variables.

Equipment required for each subject:

- Investigational device
- Other components as applicable (prosthetic feet, adapters)
- Tools for fitting
- Detailed protocol
- Case report forms (CRFs) in Smart-Trial – Tablet/computer **OR** Printed out Case report forms (CRFs including instruments listed above)

The equipment used does not require specific monitoring, maintenance, or calibration procedures.

8.2 Investigational Device(s) and Comparator(s)

The subjects will be asked to use the investigational device as their primary prosthesis for **4 weeks**. Individual exposure will differ between subjects. Subjects are expected to use it for their daily living activities as they would with any other prosthesis, for up to 18 hours a day depending on the amputee. The comparator device will not be used within the timeframe of the investigation. Subjects will evaluate and provide feedback on their exposure of the comparator prior to them being fitted to the investigational device.

The comparator device will be the former version Rheo Knee (XC) or any other passive microprocessor controlled prosthetic knee (excluding Kenevo as it does not have the same intended patient population as the investigational device). They have the same intended use as the investigational device. Furthermore, they are indicated for the same condition and population group. Passive MPKs are widely accepted devices, providing clinical benefits to the user.

Where possible, the subject will be using the remaining part of their current prosthetic system with the investigational device, as it was used with the comparator device. In some cases where a subject is using components from other manufacturers (e.g. feet not validated for use with the investigational device) compatible components will be provided.

No other device, medication or intervention will be used.

Up to 13 subjects are to be enrolled and therefore 13 investigational devices will be used, as the devices are intended to be used by a single patient; one for each subject.

8.3 Subjects

All subjects will be dispositioned as follows:

- Screen Failure: Subject did not pass screening procedures, not called in for clinical visit;
- Candidate for enrollment: Passed screening procedures, accepts to come in for clinical visit;
- Enrolled: Subject signs informed consent and takes part in the first experimental session;
- Fitted: Subject leaves the clinic on the investigational device;
- Drop-out: Enrolled subject whose participation ended because they did not want to continue participation.
- Discontinued: Candidate for enrollment or Enrolled subject whose participation ended because they withdrew consent, were withdrawn by the Investigator, were lost to follow up, or died.

Table 6 Inclusion/Exclusion criteria

Inclusion:	Exclusion:
Only patients with the following characteristics are eligible for study entry:	Patients with the following characteristics are not eligible for study entry:
45Kg < body weight < 136Kg	Users with stump pain*
Cognitive ability to understand all instructions and questionnaires in the study;	Users with socket problems**
Unilateral TF/KD amputees that are regular prosthesis users for at least 3 months	Pregnant Users***
Current MPK users (passive MPKs only) regularly performing descent activities (stairs/ramps)	Users using Power Knee, Kenevo or mechanical knees as their prescribed prosthesis
Age \geq 18 years	Alignment that cannot be matched with the Navii setup, as described in Instructions for use.
Willing and able to participate in the study and follow the protocol	-Osseointegration

*Question on pain affecting their functional ability (yes/no)

**Socket fit: Socket fit comfort score over 5

*** Self reported

A subject can withdraw from participation at any time, at his/her discretion, and this will not have any consequences for the participant's treatment. In such cases a report stating reasons for discontinuation of the participant shall be prepared by the **LPI**. No further investigational procedures concerning the subject will be conducted, except for a statement explaining the reason for withdrawal, including but not limited to: interacting or interviewing the subject in order to obtain data on him/her; obtaining additional private information on the subject by either observing the subject or collecting or receiving such information from any source.

The **LPI** can withdraw the participant from the trial at any time. The reasons shall be documented. There are no pre-specified criteria for discontinuation of participants from the trial. The discontinuation of participants in the trial will not result in replacement with new participants. If withdrawal is due to problems related to the investigational device the participant will be asked for permission to follow the status/condition outside the clinical investigation. The follow-up will be individualized.

Screening will be supported by Össur customers (prosthetic clinics) with potential for users fitting into the inclusion criteria.

Enrollment will take place at the Össur site in Orlando.

The total time period required to implement the clinical investigation is expected to be 12 weeks. Each individual subject is expected to participate in the clinical investigation for 4 weeks. The estimated time needed to include this number (enrolment period) is 6 weeks.

At least 10 subjects are required to finish the protocol for statistical data analysis, as specified in chapter **10.2 Sample size calculation**.

